The number of subjects included in the Omegaven® group will be based on a compassionate use protocol and not on study power considerations. The number of subjects included in the soybean oil fat emulsion historical cohort group will not be based on study power considerations but rather on the number of eligible subjects from a pre-existing cohort.

The primary safety analysis will be descriptive and not based on statistical significance. However, in Table 4 we outline power to detect several differences in the frequency of adverse events, assuming 20, 25, or 30 patients, diverse proportion of subjects with adverse event in either treatment period and not with the adverse event in the other (proportion of discordant pairs), for a two-sided 5% significance level McNemar's tests. Table 5 includes estimates of power for a Fisher's exact test when comparing Omegaven® with historical control groups, assuming diverse frequency of occurrence of the adverse event in the control group, equal number of subjects in each group, and diverse differences in proportions between Omegaven® and soybean oil fat emulsion groups.

For lower proportions of discordant pairs, we would generally attain close to 80% power in McNemar's test. Even for higher proportions of discordant pairs, assuming the high differences between before and after treatment that we expect to observe, e.g., 50% or more, 80% power can be attained in McNemar's test (Table 4). In Fisher's exact test, we will attain 80% power or more to detect differences between Omegaven® and historical controls of 45% or larger, regardless of the frequency of adverse events in each group (Table 5).

Table 4 – Power to detect varying differences in proportions before and after treatment with Omegaven® in a McNemar's test. All calculations were based on an alpha significance level of 0.05.

Difference between proportions	Proportion of discordant pairs	McNemar's Test		
		Sample size in the Omegaven™ group		
		20	25	30
30%	40%	59%	72%	81%
	60%	44%	55%	63%
50%	60%	92%	97%	99%
	80%	79%	88%	93%
80%	85%	>99%	>99%	>99%
	95%	>99%	>99%	>99%

*Calculations performed Statxact.

Table 5 – Power to detect varying differences in proportions between Omegaven® and historical control groups in a Fisher's exact test. All calculations were based on an alpha significance level of 0.05.

Differences in the frequency of the event between Omegaven® and historical control groups	Frequency of the event in one of the comparison groups	Fisher's Exact Test		
		20	25	30
35%	5%	72%	82%	89%
	25%	49%	65%	72%
	50%	57%	68%	78%
45%	5%	89%	95%	98%
	25%	73%	88%	92%
	50%	89%	95%	98%

*Calculations performed using N-query advisor.

e. Study Organization

[name] will serve as the principal investigator. [name] will serve as the managing co-investigator. [name], [name], [name], [name], and [name] will assist with patient enrollment. Drs. [name], [name], and [name] along with the CRP staff will assist in study design and data analysis. Data collection will be done by the research nurses, with assistance from the nursing unit liaisons, the study coordinator, and research assistants in [name] lab. All individuals who assist in this function will have CITI training. The necessary CCI amendments and approvals will be obtained prior to any staff assisting in this function. The study coordinator will abstract the medical records and complete the CRFs and a careful QC visual inspection of the CRFs prior to submitting them for data entry. The Research Coordinator will complete all data entry..

f. Data and Safety Monitoring Plan

Patients will be monitored while receiving Omegaven® treatment to observe for signs of Omegaven® toxicity. At the start of Omegaven® therapy, patients will be monitored closely during and shortly after initial Omegaven® administration to observe for signs of allergic reaction and anaphylaxis. In the event the patient demonstrated signs or symptoms of allergic reaction, the Omegaven® will be discontinued and the PI and attending physician will be notified. Selected safety labs will be evaluated by attending staff

and the Study Investigators for both clinical and research purposes. Blood samples will be taken prior to the start of therapy (baseline), and thereafter in accordance with the scheduled represented in the tables below.

Reversal/Safety Study Lab Schedule:

Patient Status	Parameter	Tests to be Performed	Frequency
Inpatient/receiving Omegaven®	Direct bilirubin >2 mg/dL	PN profile, AST, GGT, CRP, lipid Panel, PT, PTT, INR, fibrinogen, EFA Panel	Weekly
	Direct bilirubin ≤2 mg/dL	PN profile	Weekly
		PN profile, AST, GGT, CRP, PT, PTT, INR, fibrinogen, EFA panel, lipid panel	Monthly
Inpatient/off Omegaven®			
		PN profile, AST, GGT, CRP, lipid Panel, PT, PTT, INR, fibrinogen, EFA Panel	one complete set of post-Omegaven labs
Outpatient/on Omegaven®	Direct bilirubin ≥ 2 mg/dL	PN profile, AST, GGT, CRP, lipid Panel, PT, PTT, INR, fibrinogen, EFA Panel	Weekly
	Direct bilirubin ≤2mg/dL	PN profile, AST, GGT, CRP, lipid Panel, PT, PTT, INR, fibrinogen, EFA Panel	Monthly until off Omegaven and at least 1 direct serum bilirubin < 2 mg/dL

*minimum requirements, may be performed more frequently for routine clinical care

If under the discretion of the principal investigator the patient is able to return home and receive Omegaven®, the patient is required to return to Boston every 2 months or other mutually agreed upon schedule for evaluation and follow up. The Principle Investigator also requires for arrangements to be made through the patient's home health care agency for the required weekly or monthly blood draws the patient will need while at home in order to remain on Omegaven®. The lab results then must be faxed to Children's Hospital Boston in a timely manner. Additionally, measures will be taken to decrease the chance of administration errors when Omegaven® is given in the home. Families will be provided with a letter outlining strategies for reducing medication administration errors, such as independent double-checks. Also, families will be provided with fish stickers to be affixed to their Omegaven® pump to decrease the likelihood of using the incorrect pump to administer Omegaven®.

Dose reduction will occur if there is evidence of lipid intolerance (serum triglycerides > 200mg/dL) or evidence of bleeding. Growth indices include weight, length, and head circumference will also be monitored.

Other standard care laboratory results will be captured for the Omegaven® protocol. These are listed along with the standard schedule in Table 3.

The frequency of laboratory monitoring may be reduced to monthly or as clinically necessary, for patients who have been on a stable regimen of Omegaven® for a minimum of 4 months and whose serum bilirubin and hepatic enzymes have normalized.

The CAIR team completes rounds every Wednesday morning on all inpatient short bowel patients which incorporates all Omegaven® study patients. A complete comprehensive case review for all inpatients receiving Omegaven® therapy under the compassionate-use protocol and any outpatients issues are discussed among the CAIR team and with [name], [name], and the Omegaven® study nurses. All pertinent medical, nutritional, and psychosocial outpatient information is reviewed during these case reviews.

This study will be monitored by an independent data safety monitoring board (DSMB). The DSMB will have 6 members [([name] (Chair), [name], [name], [name] (BIDH), Senior level statistician TBD, and [name] RN.)] The DSMB will be chaired by a physician and surgeon who is not part of the Clinical Nutrition Service at Children's Hospital, Boston. The Board will also include a CHB gastroenterologist and an external member from the Beth Isreal Deaconess Hospital. The Chair will receive copies of all adverse events reports and may call a DSMB meeting based on the reports received. The DSMB will meet formally every 6 months to review preliminary safety data. Prior to this, the Investigators had undergone periodic review by the CCI and met with the GCRC staff to discuss preliminary findings and address safety concerns, including infection rates and medication errors.

The responsibilities of this board will include:

Analysis of the success and safety of the experimental therapy. Success will be measured by each patient's improvement in biochemical markers and avoidance of end stage liver failure.

Review the research protocol, and amendments, informed consent documents, and plans for data and safety analysis.

Evaluate the progress of the intervention, including assessment of data quality and timeliness of data entry, participant recruitment, accrual and retention, and any other factors that may affect the study outcome.

Review any factors external to the study when relevant, such as scientific or therapeutic developments that may have an impact on the safety of the subjects or the ethics of the trial.

Ensure the confidentiality of the trial data.

The DSMB will be able to contact the investigators at any time by telephone or pager to facilitate adequate feedback of information to medical decision-makers. This will ensure that research felt to involve excessive risk in relation to anticipated benefits is terminated appropriately. To prevent potential or real conflicts of interest, if the research procedure is deemed by the DSMB to involve excessive risk in relation to anticipated benefits, the investigators will be contacted by phone or pager. The research will then be suspended pending further investigation, or terminated at the suggestion of the Board.

6. Risks and Discomforts

Potential Risk of Omegaven® Treatment

Omegaven® has been studied in animal pre-clinical models as well as Phase I, II, III, and post marketing human trials in both Europe and Asia. Prolonged bleeding time and an inhibited platelet aggregation can occur. It should not be administered to patients known to be allergic to fish or egg protein.

Contraindications to Omegaven® include the following:

- Impaired lipid metabolism
- Severe hemorrhagic disorders
- Unstable diabetes mellitus
- Collapse and shock
- Stroke/ Embolism
- Recent cardiac infarction
- Undefined coma status

Side effects:

The infusion of Omegaven® can lead to a prolonged bleeding time and an inhibited platelet aggregation. In rare cases, patients may experience a fishy taste.

The administration of Omegaven® should be stopped or reduced if there is a marked increased in blood glucose levels during the Omegaven® infusion. Undesirable effects that are seen during the infusion of Omegaven® that may also occur with conventional fat emulsions (i.e., Intralipid®) include:

- Slight rise in body temperature
- Heat sensation and/or cold sensation
- Chills
- Flushing or cyanosis
- Lack of appetite, nausea, vomiting
- Dyspnea
- Headache, pain in the chest, bone pain
- Priapism
- Increase/decrease blood pressure
- Anaphylactic reactions/erythema

Other expected adverse events that are common to all patients with short bowel syndrome, regardless of the type of fat emulsion they receive, include blood stream infections and re-admittance to hospital.

Causes for re-hospitalization include dehydration, bloodstream infections, electrolyte abnormalities, bowel obstruction, and central venous catheter malfunction.

Overdose:

In the event of an overdose of Omegaven®, there is a risk of developing fat overload syndrome that may occur when the triglyceride level rises >200 mg/dL acutely as a result of too rapid a rate of infusion, or chronically at high infusion rates in associated with a change in the patient's clinical condition (e.g., renal dysfunction, sepsis). In such cases, the infusion should be stopped or, if necessary, continued at a reduced dose. Metabolic acidosis has occurred in patients receiving Omegaven® at excessive doses without simultaneous administration of dextrose.

Potential Benefit of Omegaven® Treatment

Omegaven® may be effective in stabilizing or reversing hepatic injury associated with the use of parenteral nutrition. It may allow the patient to continue to receive the majority of his/her caloric intake from parenteral nutrition while advancing on enteral nutrition or awaiting liver or liver/intestinal transplant

Potential Risks of No Treatment

Since Omegaven® will only be offered to those patients for whom no standard therapy is likely to safe and effective, the risks of not being treated are those allowing for the natural history of their disease and associated clinical manifestations to progress. These include fulminate liver failure and death.

Summary – Overall Risk Assessment

Patients will be at some risk inherent in taking a pharmaceutical agent that has not been fully evaluated for long duration treatment. However, the availability of safety data demonstrates no life-threatening risks or toxicities to vital organs or physiologic functions. Prolonged bleeding times and inhibition of platelet aggregation are a potential risk, especially to those patients with an underlying coagulopathy or those being treated with an anticoagulant. The potential benefits of Omegaven® in this patient population are mainly based on the experimental evidence and a single case of dramatic success. However, the study will only be available to those for whom no standard therapy is available or appropriate, or has already failed. The risks and potential benefits will require careful individual assessment by both the investigators and patients. The heterogeneity of clinical manifestations will lead to non-uniform risk-benefit ratios across the eligible patient population.

7. Potential Benefits

The potential benefits of this study apply directly to the patient in question and to possible improvement in the treatment of future patients. If successful, the experimental treatment will provide a safe and effective means of avoiding liver failure requiring transplant or that may lead to death. Thus, the potential complications of surgery or fulminant hepatic failure may be avoided.

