- a) The patient will be PN dependent and at risk for significant hepatic injury due to prolonged use of parenteral nutrition.
- b) Have significant hepatic dysfunction due to parenteral nutrition despite utilization of all conventional therapies.

Inclusion Criteria:

1. Patients will be PN dependent (unable to meet nutritional needs solely by enteral nutrition) and are expected to require PN for at least another 30 days
2. Patients considered eligible for study participation must have parenteral nutrition associated liver disease (PNALD) as defined as a direct bilirubin of ≥ 2 mg/dl or currently on Omegaven through another protocol. Other causes of liver disease should be excluded. A liver biopsy is not necessary for treatment.
3. Direct bilirubin > 2.0 mg/dl, or already on Omegaven through another protocol.
4. Signed patient informed consent.
5. The patient must have utilized standard therapies to prevent the progression of his/her liver disease including surgical treatment, cyclic PN, avoiding overfeeding, reduction/removal of copper and manganese from PN, advancement of enteral feeding, and the use of ursodiol (i.e., Actigall[®]).

Exclusion Criteria:

1. Pregnancy
2. Other causes of chronic liver disease (Hepatitis C, biliary atresia, and alpha 1 anti-trypsin deficiency,)
3. Enrollment in any other clinical trial involving an investigational agent (unless approved by the designated physicians on the multidisciplinary team)
4. The parent or guardian or child unwilling to provide consent or assent

In rare instances, patients diagnosed with PNALD may later be found to have liver disease due to other causes in addition to the use of PN (i.e., inborn errors of metabolism, viral infections). Such causes may not be known at the time of enrollment and will not preclude them from continuing in the study. For the sake of statistical analysis, however, these patients will be excluded although all data will be collected and reviewed.

Screening Procedures

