Because both Intralipid® and Liposyn® II are isotonic, both could be infused through either a central or peripheral line. Both products are compatible with parenteral nutrition solutions and were co-infused via y-site. Source container hang times varied during this period, and IFE was either infused from a single container over 24 hours or the container was changed every 12 hours per CDC recommendations. Also during this period, the administration method of PN changed. Prior to 1999, standard 0.2 micron inline filters were used routinely and only PN but not IFE could be infused through them (IFE was infused via y-site beneath the filter). After 1999, 1.2 micron filters became the standard inline filter, allowing for IFE to be filtered along with the PN solution.

Duration of Therapy

Patients remained on either Liposyn® II or Intralipid® until weaned from PN.

Discontinuation of Therapy

Patients at risk for malnutrition or resumption of PN were typically followed by the Clinical Nutrition Service for several months following discontinuation of PN.

ADDITIONAL PREDICTORS OF INTEREST

Since decisions about starting Omegaven® administration will follow a compassionate protocol, we expect that patients receiving Omegaven® will present more severe liver disease than the controls from the historical cohort. Therefore, to correct confounding biases, we anticipate the need to adjust for potential predictors of liver outcomes at baseline. Baseline will be defined as: the date that treatment starts for Omegaven® patients and on the date that patient reached bilirubin levels > 2 for soybean based fat emulsion patients.

The following predictors of liver disease will be considered:

- Baseline direct bilirubin levels.
- Diagnosis of Necrotizing Enterocolitis (vs. any other disease)
- Gender (male vs. female)
- Age (≥ 8 months vs. < 8 months)
- Gestational age
- Birth weight
- Race

To assess patients comparability, we will also descriptively explore trends in direct bilirubin level before the beginning of follow-up (start of treatment date for Omegaven® patients and date in which direct bilirubin level raised to > 2 mg/dL for control patients)

Subgroup Analysis

With exploratory purposes, we will describe safety and/or efficacy of Omegaven® in subgroups of patients including younger (vs. older) patients at baseline, patients who presented with infections (vs. who did not),

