Analysis of Baseline Characteristics

For statistical purposes, baseline values will be defined as the last measurement before starting to administer Omegaven® for patients, in the treatment group, and as the measurement taken when a patient first had a direct bilirubin level > 2 mg/dL recorded, in the historical control group. Descriptive statistics for all baseline relevant risk factors will be summarized for Omegaven® (omega-3 based fat emulsion) and historical control (soybean oil fat emulsion) groups. Associations between categorical predictors and Omegaven® vs. soybean oil fat emulsion groups will be tested through chi-square tests. Associations between continuous predictors and treatment groups will be studied through means (and standard deviations) and t-tests, or medians (and interquartile ranges) and Wilcoxon tests, when appropriate.

Analysis of Safety and Tolerability of Omegaven®

All primary safety and tolerability analyses will be based on descriptive statistics. In secondary analyses, we will also assess the statistical significance of differences. Some safety and tolerability outcomes will be measured only in the Omegaven® group. For those, we will compare results before starting PN with Omegaven® (while receiving PN with soybean oil fat emulsions) with after starting PN with Omegaven®. The period receiving Omegaven® will start to be counted 30 days after beginning PN with Omegaven® for the main analysis. Outcomes measured in the Omegaven® and soybean oil fat emulsion groups will be described separately for each of those groups for a period starting 30 days after baseline, i.e., 30 days after starting PN with Omegaven®, for the treatment group, and 30 days after bilirubin > 2 mg/dL, for the soybean oil fat emulsion group.

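### Patients already on Omegaven elsewhere can enter with no bilirubin requirement, and the plan does not say how, or whether, they count in the time-to-normalization analysis

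*Combined protocol and SAP*

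**What the plan says.** **Entry to the Omegaven group** (section b, Patient Selection and Inclusion/Exclusion Criteria). Criterion 2 requires PN-associated liver disease "as defined as a direct bilirubin of ≥ 2 mg/dl or currently on Omegaven through another protocol". Criterion 3 requires a direct bilirubin above 2.0 mg/dL, "or already on Omegaven through another protocol". Transfers must still meet the other criteria: they must be PN dependent and "are expected to require PN for at least another 30 days", must have used standard therapies, and must not meet an exclusion criterion.

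**Removal from analysis.** The same section states one exclusion of enrolled patients from the statistics, for those later found to have another cause of liver disease: "For the sake of statistical analysis, however, these patients will be excluded although all data will be collected and reviewed". Transfers are not mentioned.

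**Time zero and baseline.** Under Additional Predictors of Interest, baseline is "the date that treatment starts for Omegaven® patients and on the date that patient reached bilirubin levels > 2" for soybean patients. The endpoint section repeats this. Section 5c, Analysis of Baseline Characteristics, adds that "baseline values will be defined as the last measurement before starting to administer Omegaven® for patients" in the treatment group.

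**Endpoint and method.** Section 5c, Analysis of Efficacy, uses time from baseline to the first of three consecutive values below 2 mg/dL. The endpoint section also accepts one value at or below 2 together with weaning. The methods are Kaplan-Meier, log-rank and Cox. Patients who die or are transplanted before normalizing get an infinite time to event.

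**Controls.** The first historical cohort is restricted to patients whose direct bilirubin was ever above 2 mg/dL. The contemporary cohort qualifies at 2.0 mg/dL or more, with criteria applied when cholestasis develops. Neither has an alternative route in.

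**The concern.** Hypothesis 2.1 compares how fast patients come back to 2 mg/dL or below after having exceeded it. A transfer need not have exceeded it, either at entry or before the first dose. A transfer's early course on Omegaven also lies outside this study: anyone who died, was transplanted or came off PN before reaching this protocol cannot be enrolled. This is a prevalent-user problem, and the plan specifies ordinary survival methods with no left truncation.

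At stake is the primary efficacy comparison. It is already non-randomized and rests on the two groups having comparable starting points. The limitations section discusses differential severity only as a bias against Omegaven and does not mention this route.

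**Working it through.** No stated figure bears on this point: there is no efficacy sample size, event rate or count of transfers. The check follows a transfer through the rules under each possible time zero. All rates below are assumptions.

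**Reading A: clock starts at the original first dose.** The baseline wording points this way, because for someone already on Omegaven the last measurement before starting it predates enrolment here. To be enrolled, the patient must be alive, untransplanted and still on PN. Two groups are therefore missing:
- early deaths and transplants, which the plan ranks as infinite time; their absence favours Omegaven;
- early normalizers who were weaned, who are the fastest successes; their absence works against Omegaven.

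The balance was checked with no true effect, using:
- normalization hazard λN = ln 2 / 20 = 0.0347 per week;
- 30% die or are transplanted first, so λD = λN × 0.3/0.7 = 0.0149;
- transfer 4 to 52 weeks after first dose;
- weaning at an exponential delay after normalization.

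All patients normalized by week 26: 0.70 × (1 − exp(−(0.0347 + 0.0149) × 26)) = 0.70 × 0.72 = 51%. By week 104 it is 70%. Among transfers still on PN at entry (simulated):

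| Mean delay to weaning | Normalized by week 26 | By week 104 |
|---|---|---|
| 8 weeks | 37% | 76% |
| 16 weeks | 45% | 80% |
| 30 weeks | 52% | 83% |
| 60 weeks | 58% | 85% |

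With prompt weaning, transfers look slower than the true 51% at week 26; with slow weaning they look faster. At week 104 they look better in every row. The direction thus depends on weaning and death rates that the documents do not give, and on the follow-up time examined.

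If weaning is ignored, only the missing failures act. A simulation on the same rates (30 or 50 per group, 104 weeks, 2000 replicates, no true effect) then gives hazard ratios of about 1.03, 1.10, 1.15 and 1.25 with transfers at 10, 20, 30 and 50% of the Omegaven group. False positives favouring Omegaven are about 3, 4–5, 7–8 and 10–16%, against a nominal 2.5%. These figures describe one side of the selection only.

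**Reading B: clock starts at entry here.** A transfer may already be at or below 2 mg/dL, so the event is immediate or undefined. Suppose 25% of the other patients normalize by week 4, and a fraction f of the group enters already normalized. The apparent week-4 rate is (1 − f) × 25% + f:
- f = 10%: 0.9 × 25% + 10% = 32.5%;
- f = 20%: 0.8 × 25% + 20% = 40%.

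The same simulation, again without weaning, gives hazard ratios of about 1.09, 1.19, 1.31 and 1.55 for 10, 20, 30 and 50% transfers. False positives are about 5, 8–12, 13–19 and 31–47%.

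**With transfers excluded,** the simulated hazard ratio is about 1.0 and the false-positive rate 2.0–2.5%.

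**The case against.** The strongest counter-argument concerns direction. A reader might infer that the waiver biases the comparison toward Omegaven however time zero is read. The documents do not support that. Patients stay on Omegaven until weaned, entry requires at least 30 further expected days of PN, and normalization with weaning is itself an endpoint. Under reading A the selection therefore removes fast successes as well as failures. This objection stands.

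A reader might also infer that controls carry no survivor condition. That is wrong for the first cohort, which was defined by at least 90 days of PN dependence. A control whose bilirubin passed 2 mg/dL before day 90 had to remain alive and on PN to be counted. The condition differs, since it does not run from treatment start, but the asymmetry is not one-sided.

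Three further points limit the size. Transfers may be few. The other protocol may have had its own bilirubin threshold. Some pages around the design section are not in the available copy. The plan also calls its efficacy evidence preliminary, sets no efficacy sample size, and names non-comparability as its main limitation.

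Two possible safeguards fall short. Hypothesis 2.1 implies a start above 2 mg/dL but is not turned into an analysis-set rule. Adjustment for baseline bilirubin cannot restore patients who never enrolled.

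**Conclusion.** The concern holds as a gap in the definition of the efficacy set and of time zero. As written, the plan allows patients with no qualifying bilirubin, or with an unobservable early course, into a comparison premised on starting above 2 mg/dL.

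Under the first-dose reading, which the baseline wording favours, the estimate is open to bias of unknown direction. Under the entry-date reading the bias favours Omegaven, and the 32.5% and 40% figures apply only there. They assume that the counted transfers are all at or below 2 mg/dL on entry and that the rest normalize at the same 25%. The actual size cannot be stated without the number of transfers and their bilirubin before Omegaven. The point should be settled before analysis; it does not by itself invalidate the study.

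**What to change.** In section 5c:

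1. Define the primary efficacy set as patients who started Omegaven under this protocol and whose last direct bilirubin before their first-ever dose was above 2 mg/dL.
2. State that time zero is the first-ever Omegaven dose.
3. As a sensitivity analysis, add transfers with a documented pre-Omegaven bilirubin above 2 mg/dL, with the clock at first dose and delayed entry (left truncation) at enrolment here. Those who normalized before enrolment then contribute no time at risk. Say how this combines with the infinite-time rule, since deaths before enrolment remain unseen.
4. Report the number of transfers, their time on Omegaven before enrolment and their pre-Omegaven bilirubin. Analyse the remaining transfers for safety only.
5. Add prevalent-user selection, with its uncertain direction, to the limitations, beside the 90-day PN condition of the first control cohort.

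The cost is SAP wording and fewer Omegaven patients in the efficacy analysis. No stated efficacy power depends on that number. Enrolment and access to treatment are unchanged.
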